7.8 Prescription and Normal Tissue Constraints

7.8.1 Breast CTV:

7.8.1.1 Per protocol \geq D95% will receive \geq 95% of prescription;
Variation acceptable \geq D90% receives \geq 90% of prescription

7.8.2 Tumor CTV

7.8.2.1 Per protocol D95% receives \geq 95% of dose; variation acceptable D90% receives \geq 90% of the boost dose

7.8.3 Robustness analysis for Protons

7.8.3.1 Breast CTV coverage would be evaluated for 5mm movements or 3% range changes. Per protocol Breast CTV V90% receives \geq 95% of the prescription dose; variation acceptable \geq V90% receives \geq 90% of the prescription dose.

7.8.3.2 Under the same robustness evaluation criteria, plans will be evaluated for D max. Variation acceptable D0.01cc % \leq 120%

Protons DVH summary table

		Goal	Major violation
Breast CTV		\geq V95% will receive \geq 95% of prescription	V90% $<$ 90% of prescription
		Dmax $<$ 107%	Dmax $>$ 115%
Tumor CTV		\geq V95% will receive \geq 95% of prescription	V90% $<$ 90% of prescription
		Dmax $<$ 107%	Dmax $>$ 115%
Breast CTV robustness		V90% $>$ 90% of prescription	V90% $<$ 90% of prescription
Heart	Max dose	\leq 25% of prescription	$>$ 33% of prescription
	Mean	$<$ 0.1Gy	$>$ 1Gy

Breast Skin	Max dose	$\leq 105\%$ of prescription	$> 110\%$ of prescription
Lung Ipsilateral	V50% of prescription	$\leq 10\%$	$> 15\%$
	V20	record	
Lung contralateral	V50%	$\leq 7\%$	$> 10\%$
Lung Total	Mean dose	record	
	V20Gy	record	
	V50%	record	
LAD (optional)	Mean dose	record	
	Max dose	record	
RCA	Mean dose	record	
	Max dose	record	

Photons (x-rays) DVH summary table

		Goal	Major violation
Breast CTV		$\geq V95\%$ will receive $\geq 95\%$ of prescription	$V90\% < 90\%$ of prescription
		Dmax $< 107\%$	Dmax $> 115\%$
Tumor CTV		$\geq V95\%$ will receive $\geq 95\%$ of prescription	$V90\% < 90\%$ of prescription
		Dmax $< 107\%$	Dmax $> 115\%$
Breast CTV robustness		$V90\% > 90\%$ of prescription	$V90\% < 90\%$ of prescription
Heart	Max dose	$\leq 33\%$ of prescription	$> 50\%$ of prescription
	Mean	$< 1\text{Gy}$	$> 2\text{Gy}$
Breast Skin	Max dose	$\leq 107\%$ of prescription	$> 115\%$ of prescription
Lung Ipsilateral	V50% of prescription	$\leq 10\%$	$> 15\%$
	V20	record	
Lung contralateral	V50%	$\leq 7\%$	$> 10\%$
Lung Total	Mean dose	record	
	V20Gy	record	
	V50%	record	
LAD (optional)	Mean dose	record	
	Max dose	record	
RCA	Mean dose	record	
	Max dose	record	

7.9 Quality Assurance Documentation

7.9.1 At a minimum, the initial 3 treatment plans per physician will be centrally reviewed by the principal investigator or designee prior to the start of treatment.

7.10 Axillary management

7.10.1 Only clinical N0 patients are eligible. If 2 or less positive LN are found in the SLNB without ECE no additional radiation would be considered

7.11 Surgery

7.11.1 Surgical treatment will be done at the discretion of the treating surgeon.
7.11.2 Surgery will be done at 8 weeks after the completion of radiation.
Acceptable range is 4-16 weeks after.

7.12 Endocrine therapy or chemotherapy

7.12.1 Systemic management would be done at the discretion of the treating medical oncologist after the surgery

8 Radiotherapy Dose Modifications Based on Adverse Events

This study has no pre-specified interruptions due to adverse events. Treatment interruptions are discouraged. No dose modifications should be done for treatment interruptions.

9.0 Ancillary Treatment/Supportive Care

Skin changes are common complications of breast cancer radiation therapy. Usual care will be provided as per the treating institution's standard of practice. If the skin becomes erythematous and/or there is pruritus, topical steroid cream may be prescribed. The addition of antihistamines may be used for severe pruritus. Patients experiencing pain will be prescribed pain medication.

10.0 Adverse Event (AE) Reporting and Monitoring**10.1 Definitions**

Adverse Event- An untoward or undesirable experience associated with the use of a medical product (i.e. drug, device, biologic) in a patient or research subject.

Serious Adverse Event – Any grade 4 or 5 adverse event as defined by CTC AE v4.0. Adverse events are classified as serious or non-serious. Serious problems/events can be well defined and include in general:

- Death
- Life threatening adverse experience where emergent lifesaving treatment is necessary.

Unanticipated Problems Involving Risks to Subjects or Others (UPIRTSO)- Any unanticipated problem or adverse event that meets the following three criteria:

Serious: Serious problems or events that results in significant harm, (which may be physical, psychological, financial, social, economic, or legal) or increased risk for the subject or others (including individuals who are not research subjects). These include: (1)

death; (2) life threatening adverse experience; (3) hospitalization - inpatient, new, or prolonged; (4) disability/incapacity - persistent or significant; (5) birth defect/anomaly; (6) breach of confidentiality and (7) other problems, events, or new information (i.e. publications, DSMB reports, interim findings, product labeling change) that in the opinion of the local investigator may adversely affect the rights, safety, or welfare of the subjects or others, or substantially compromise the research data, **AND**

Unanticipated: (i.e. unexpected) problems or events are those that are not already described as potential risks in the protocol, consent document, not listed in the Investigator's Brochure, or not part of an underlying disease. A problem or event is "unanticipated" when it was unforeseeable at the time of its occurrence. A problem or event is "unanticipated" when it occurs at an increased frequency or at an increased severity than expected, **AND**

Related: A problem or event is "related" if it is possibly related to the research procedures.

Preexisting Condition- A preexisting condition is one that is present at the start of the study. A preexisting condition should be recorded as an adverse event if the frequency, intensity, or the character of the condition worsens during the study period. At screening, any clinically significant abnormality should be recorded as a preexisting condition. At the end of the study, any new clinically significant findings/abnormalities that meet the definition of an adverse event must also be recorded and documented as an adverse event.

10.2 Recording Adverse Events

CTCAE term (AE description) and grade: The descriptions and grading scales found in the revised NCI Common Terminology Criteria for Adverse Events (CTCAE) version 4.0 will be utilized for AE reporting unless as otherwise stated in the table below.

All appropriate treatment areas should have access to a copy of the CTCAE version 4.0. A copy of the CTCAE version 4.0 can be downloaded from the CTEP web site:

10.21 Adverse event monitoring and reporting is a routine part of every clinical trial. First, identify and grade the severity of the event using the CTCAE version 4.0. Next, determine whether the event is expected or unexpected and if the adverse event is related to the medical treatment or procedure. With this information, determine whether the event must be reported as an expedited report (see Section 10.3).

10.22 Assessment of Attribution

Only G4 or G5 adverse events will require an attribution. Any change in the grade of an adverse event within the list of monitored AEs will be recorded and considered to be related to treatment. Any new adverse not listed occurring within the Radiated area or in close proximity will be graded and attribution defined by the study PI.

Events determined to be possibly, probably or definitely attributed to a medical treatment suggest there is evidence to indicate a causal relationship between the treatment and the adverse event.

10.3 Reporting of Serious Adverse Events and Unanticipated Problems

When an adverse event has been identified, the study team will take appropriated action necessary to protect the study participant and then complete the Study Adverse Event Worksheet and log. The sponsor-investigator will evaluate the event and determine the necessary follow-up and reporting required.

- a. Serious Adverse Events will be reported as part of regular adverse event reporting mechanisms via the data capture system and logged for review reporting.

10.31 Investigator Reporting: Notifying the Mayo IRB:

The IRB requirements reflect the guidance documents released by the Office of Human Research Protections (OHRP), and the Food and Drug Administration (FDA) in early 2007 and are respectively entitled “Guidance on Reviewing and Reporting Unanticipated Problems Involving Risks to Subjects or Others and Adverse Events” and “Guidance for Clinical Investigators, Sponsors, and IRBs: Adverse Event Reporting – Improving Human Subject Protection.”

10.311	According to Mayo IRB Policy any serious adverse event (SAE) which the Principal Investigator has determined to be a UPIRTSO must be reported to the Mayo IRB as soon as possible but no later than 5 working days after the investigator first learns of the problem/event.
10.312	NonUPIRTSO – the investigator reports problems or events that do NOT meet criteria of an UPIRTSO in summary format at the time of the next continuing review. The investigator monitors the severity and frequency of subsequent nonUPIRTSOs.

Consider the following information to collect when developing any forms for documentation of adverse events.

Example

Information collected on the adverse event worksheet (and entered in the research database):

- Subject's name:
- Medical record number:
- Disease/histology (if applicable):
- The date the adverse event occurred:
- Description of the adverse event:
- Relationship of the adverse event to the research (drug, procedure, or intervention):
- If the adverse event was expected:
- The severity of the adverse event: (use a table to define severity scale 1-5)
- If any intervention was necessary:
- Resolution: (was the incident resolved spontaneously, or after discontinuing treatment)
- Date of Resolution:

The investigator will review all adverse event reports to determine if specific reports need to be made to the IRB and FDA. The investigator will sign and date the adverse event report when it is reviewed. For this protocol, only directly related SAEs/UPIRTSOs will be reported to the IRB.

10.4 Adverse events to be graded at each evaluation and pretreatment symptoms/conditions to be evaluated at baseline per the CTCAE v4.0 grading unless otherwise stated in the table below:

System (SOC)	Organ Class	Adverse event/Symptoms	Baseline	Each evaluation	Grading scale (if not CTCAE)
General		Pain	X	X	CTCAE
Skin and subcutaneous tissue disorders		Dermatitis Radiation	X	X	CTCAE
		Skin hyperpigmentation	X	X	CTCAE
		Skin hypopigmentation	X	X	CTCAE
Musculoskeletal		Fibrosis	X	X	CTCAE
Vascular		Lymphedema	X	X	CTCAE
Respiratory, thoracic and mediastinal disorders		Pneumonitis	X	X	CTCAE

10.5 Submit via appropriate *reporting mechanisms* the following AEs experienced by a patient and not specified in Section 10.4:

10.52 Grade 4 and 5 AEs regardless of attribution to the study treatment or procedure.

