16.6 Data & Safety Monitoring

16.61 The study chair(s) and the study statistician will review the study at least twice a year to identify accrual, adverse event, and any endpoint problems that might be developing. The Mayo Clinic Cancer Center (MCCC) Data Safety Monitoring Board (DSMB) is responsible for reviewing accrual and safety data for this trial at least twice a year, based on reports provided by the MCCC Statistical Office.

16.62 Adverse Event Stopping Rules: The stopping rules specified below are based on knowledge available at study development. We note that the Adverse Event Stopping Rule may be adjusted in the event of either (1) the study re-opening to accrual or (2) at any time during the conduct of the trial and in consideration of newly acquired information regarding the adverse event profile of the treatment(s) under investigation. The study team may choose to suspend accrual because of unexpected adverse event profiles that have not crossed the specified rule below.

Accrual will be temporarily suspended if at any time we observe the following events that are possibly, probably or definitely related to treatment:

If 4 or more patients in the first 10 treated patients or 6 patients at any point in the study experience (end/during radiation, 3 months after radiation, at 12 months and yearly after) a grade 3 or higher skin induced radiation dermatitis, pain over the treated area, swelling over the breast area, pneumonitis, radiation in-field wound infection, or poor cosmetic outcome (change from excellent/good cosmesis to fair or poor, or from fair to poor via Harvard cosmesis scale).

We note that we will review grade 4 and 5 adverse events deemed “unrelated” or “unlikely to be related”, to verify their attribution and to monitor the emergence of a previously unrecognized treatment-related adverse event. However, any grade 4 or higher regardless of the attribution could be used for temporary suspension of the protocol at that time. The study team will review all grade 4 or 5 AEs, if they are clearly “unrelated” the study can remain active while the MCCC reviews the adverse event. In all other cases the grade 4 or 5 toxicity will determine a temporary closure of the study while it is reviewed by the MCCC DSMB.

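### Section 10.3 limits IRB reports to directly related events, which contradicts the possibly-related test in 10.1 and the reporting rules in 10.311 and 10.312

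*Combined protocol and SAP*

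**What the plan says.** Four parts of the protocol govern what reaches the IRB.

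- **Section 10.1, SAE.** An SAE is "Any grade 4 or 5 adverse event as defined by CTC AE v4.0". The short list that follows names only death and life-threatening events.
- **Section 10.1, UPIRTSO.** The event must be serious, unanticipated and related. Serious has no grade threshold and includes "hospitalization - inpatient, new, or prolonged". Related is met when the event is "possibly related to the research procedures".
- **Sections 10.311 and 10.312.** Under 10.311, "any serious adverse event (SAE) which the Principal Investigator has determined to be a UPIRTSO must be reported" to the IRB no later than 5 working days after the investigator learns of it. Under 10.312, events that are not UPIRTSOs go to the IRB in summary at the next continuing review, and no degree of relatedness is required.
- **End of Section 10.3, after the worksheet list.** For this study, "only directly related SAEs/UPIRTSOs will be reported to the IRB".

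Two other places set a relatedness threshold. The accrual-suspension rule in 16.62 counts events that are "possibly, probably or definitely related to treatment". Section 10.532 requires later deaths to be submitted when they are thought at least possibly due to treatment.

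**The concern.** The last sentence of 10.3 is framed as specific to this protocol, so site staff would reasonably take it as the controlling rule. In ordinary usage directly related is a stricter test than possibly related. A team that follows the sentence would hold back events that 10.311 makes mandatory, and a team that follows 10.311 would break the sentence.

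What is at stake is the IRB's timely knowledge of unanticipated harm in a small single-arm study of preoperative whole-breast radiation. The primary endpoint, the decision rule and the sample size do not depend on it.

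**Working it through.** No arithmetic applies. The check takes four kinds of event through the rules as written.

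**1. Life-threatening grade 4 event, not on the 10.4 list, unanticipated, possibly related.**
- 10.1: it is an SAE, and it is a UPIRTSO because a possible relationship is enough.
- 10.311: report to the IRB within 5 working days.
- End of 10.3: not directly related, so no IRB report.
- Result: direct contradiction. The event is still submitted under 10.52 whatever its attribution, and reviewed under 16.62, but neither provision names the IRB.

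**2. Grade 4 event judged unrelated.**
- 10.1: it is an SAE but not a UPIRTSO.
- 10.312: summary to the IRB at continuing review.
- End of 10.3: not directly related, so no IRB report.
- Result: a second contradiction, this time with 10.312.

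**3. Grade 3 event with inpatient admission, not on the 10.4 list, unanticipated, possibly related.**
- 10.1: it is a UPIRTSO, because hospitalization makes it serious. It is not an SAE, being below grade 4 and not life-threatening.
- 10.311: worded for an SAE judged a UPIRTSO, so read literally it does not apply.
- 10.312: applies only to events that are not UPIRTSOs, so it does not apply either.
- 10.52 and the grade 4–5 review in 16.62: not triggered.
- Result: no written 5-day route, whatever is done with the last sentence of 10.3. Section 10.22 adds to the gap. It requires attribution only for grade 4 and 5 events, apart from new unlisted events in or near the irradiated area, which the study PI attributes. An unlisted grade 3 event elsewhere need not receive the relatedness judgment on which UPIRTSO status depends.

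**4. Grade 3 pneumonitis with admission.**
- 10.4 and 10.22: pneumonitis is a monitored event, and any grade change in a monitored event is deemed treatment-related.
- 10.1: an event already described as a risk is ordinarily not unanticipated. Pneumonitis is named in 2.21, 16.221 and 16.62.
- Result: ordinarily not a UPIRTSO, so it does not illustrate the gap. Only the clause in 10.1 on greater frequency or severity than expected could change that.

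**Relatedness thresholds side by side.**

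| Place | Threshold |
|---|---|
| 10.1, UPIRTSO | possibly |
| 10.532, later deaths | at least possibly |
| 16.62, accrual suspension | possibly, probably or definitely |
| End of 10.3, IRB reports | directly (undefined) |

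The first three rows are the same threshold. The last is the outlier.

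**The case against.** The best defence is that other provisions limit the harm. The investigator reviews all adverse event reports for possible IRB and FDA reporting. SAEs are logged in the data capture system. Section 10.52 requires submission of unlisted grade 4 and 5 events regardless of attribution, and 10.53 covers deaths. The DSMB sees safety data at least twice a year. Under 16.62, a grade 4 or 5 event that is not clearly unrelated closes the study temporarily pending DSMB review. All of this stands, and it rules out the inference that serious events go wholly unreported. It does not restore IRB notification or the 5-day clock, and the grade 4–5 safeguards do not reach case 3.

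A reader might also infer that the SAE and UPIRTSO definitions contradict each other. They do not: they are separate terms and may differ in scope. The heading of 10.3 names unanticipated problems as well as SAEs, its last sentence can be read as covering either, and 10.311 restates an institutional policy that is not reproduced here. The mismatch is therefore a literal gap in 10.311 and secondary to the main conflict.

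A reader might take 16.62 as yet another relatedness standard. It is not, because possibly, probably or definitely means possibly or stronger, which agrees with 10.1.

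Finally, directly related may have been meant loosely, as at least possibly related. On that reading the sentence would exclude no UPIRTSO, but it would still conflict with 10.312, and the text does not say so.

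**Conclusion.** Wrong as written, as a matter of patient-safety reporting. The firm finding is that the last sentence of 10.3 cannot be followed together with 10.1 and 10.311, or with 10.312. The secondary finding is that 10.311, read literally, gives no 5-day route for a UPIRTSO below grade 4.

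The consequence is that some UPIRTSOs may not reach the IRB, or not within 5 working days. The documents give no expected number of such events, so the size cannot be stated beyond the planned maximum of 25 patients. It would be too strong to say that every grade 3 admission, or every event rated possibly or probably related, is affected. The event must also be unanticipated, and grade changes in the 10.4 events are deemed related by rule.

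The main finding assumes that directly related has its ordinary, stricter meaning. The secondary finding assumes that SAE in 10.311 carries the definition in 10.1.

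**What to change.** Replace the last sentence of 10.3 with: *All events meeting the UPIRTSO definition in 10.1 (at least possibly related) are reported to the IRB under 10.311; other events are reported under 10.312.* Reword 10.311 so that it applies to any UPIRTSO, not only to an SAE judged to be one. When making the edit, check that 10.22 provides a relatedness judgment for every event that might be a UPIRTSO.

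The SAE definition and 16.62 need not change. Importing the whole UPIRTSO seriousness list into the SAE definition would go too far, because that list includes breaches of confidentiality and new publications, which are not adverse events.

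The cost is a few lines of protocol wording and possibly a few more IRB reports. The design and the analysis do not change.

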10.53 Grade 5 AEs (Death)

10.531 Any death within 30 days of the patient's last study treatment or procedure regardless of attribution to the study treatment or procedure

10.532 Any death more than 30 days after the patients last study treatment or procedure that is felt to be at least possibly treatment related must also be submitted as a Grade 5 AE, with a CTCAE type and attribution assigned.

11.0 Treatment Evaluation

- 11.1 Patients will be evaluated at baseline, then according to the Assessment Schedule (Section 4.0)
- 11.2 At the time of reevaluation, patients will be classified in the following manner:
 - 11.2.1 No evidence of disease (NED).
 - 11.2.2 Recurrence of disease (REC). Consider biopsy of the site and PET scan.
 - 11.2.3 The site of recurrence (or failure) will also be collected and classified as local vs. regional vs. distant recurrence.
 - 11.2.4 Secondary Treatment. The date of the first retreatment and extent of retreatment post-recurrence (i.e. secondary resection or re-irradiation for primary disease), will be collected. Pathology, if available, and operative reports are required to be submitted per Section 18.0.
- 11.3 Cosmesis evaluation and Patient Reported Outcomes
 - 11.3.1 The Harvard/NSABP/RTOG Cosmesis Scale will be used to score cosmesis by trained nurses for the primary endpoint according to the schedule outlined in section 4.0.

Excellent: Treated breast nearly identical to untreated breast

Good: Treated breast slightly different than untreated (minimal but identifiable effects of the treated breast). Mild reddening or darkening of the breast may be present. Thickening or scar tissue causes only a mild change in the shape or size.

Fair: Obvious difference in the size and shape of the treated breast. **The change involves one-quarter or less of the breast.** Severe thickening or scarring can be present.

Poor: Marked change in appearance or shape involving **more than one-quarter or less of the breast.** Treated breast seriously distorted (severe sequelae of breast tissue)
 - 11.3.2 Digital photographs should be performed according to the schedule outlined in section 4.0 and should include three poses: from the front with hands on hips, both oblique and lateral views with hands behind the back. Recommended framing should go from the sternal notch to the umbilicus. If possible, patients should be photographed against a solid colored background such as a white sheet.
 - 11.3.3 The Breast Cancer Treatment Outcome Scale (BCTOS) is a self-report instrument that has high reliability and validity and will be used for evaluating patient-rated cosmesis according to the schedule outlined in section 4.0.

11.4 Quality of life questionnaires are being done as part of the standard of care for all patients. We will correlate results of this standard of care questionnaires with clinical outcomes.

Unplanned surgical intervention will be adjudicated by a plastic surgeon and a general surgeon.

11.5 Pathologic complete response. At time of surgery the residual tumor would be measured and a score of 0-1 would be considered a pCR. Residual cancer burden (RCB) measurement is currently considered SOC for all three sites for surgical specimens after neo-adjuvant therapy. We would use the current grading used at the three Mayo sites to determine RCB.³¹

